6.4.2 Study Discontinuation

Study discontinuation is at the discretion of the Sponsor or the Investigator in any of, but not limited to, the following events:

- Occurrence of unusual AEs in terms of their nature, severity, causality, duration, or unexpected incidence.
- Medical or ethical reasons affecting the continued performance of the study.
- Difficulties in the recruitment of the subjects.

6.4.3 Stopping Rules

The sponsor (Medical Director/Chief Medical Officer) will halt the study for a review of the safety data if there are safety concerns noted for any reason and if one or more subjects experience two AE's assessed as a Grade 3 (severe) or higher, of the same type that is considered possibly, probably or definitely related to the IP.

Study Visits

The study will be conducted with a Screening visit, Day 1 / Baseline visit, Study Day visits 7, 14, 21, 28 and two follow-up visits on Days 35 and 42.

If reported violations of treatment site restrictions occurred prior to the visit at Screening, Day 1 / Baseline, Day 7, 14 or 21, details of the violation should be recorded in the CRF and the evaluations and sampling completed as scheduled.

If reported violations of treatment site restrictions occurred less than 24 hours prior to the visit at Day 28, 35, or 42, details of the violation should be recorded in the CRF and evaluations can be completed, but an additional visit 24-48 hours after the violation should be scheduled for sample collections. However, if reported violations of treatment site restrictions occurred more than 24 hours prior to the visit at Day 28, 35, or 42, details of the violation should be recorded in the CRF and the evaluations and sampling completed as scheduled.

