6.4.1 Subject Withdrawal

Participation in the study is strictly voluntary. A subject has the right to withdraw from the study at any time for any reason and is under no obligation to disclose the reason. If a subject withdraws, the Investigator and Sponsor are to be informed immediately and the withdrawal documented accordingly. Subjects may be replaced at the discretion of the Investigator and/or Sponsor.

The Investigator has the right to terminate participation of a subject at any time for any of the following:

- Use of non-permitted concomitant medication
- Lack of subject compliance
- Protocol violation
- Disease progression
- Any perceived safety risks

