6.6.3 Sample Collection

Samples for microbiologic testing will be obtained separately from both treatment targeted sites as detailed in Table 2 below. Details of sample collection, storge, and shipment can be found in the CSSSP.

Visit	Sample	Test
Screening	None	
Day 1 (Baseline - Prior to Application)	1 Swab and 12 tape sample	qPCR Bacterial Culture S. aureus CFU
Day 7	1 Swab from each treatment site	qPCR Bacterial Culture S. aureus CFU
Day 14	1 Swab from each treatment site	qPCR Bacterial Culture S. aureus CFU
Day 21	1 Swab from each treatment site	qPCR Bacterial Culture S. aureus CFU
Day 28	1 Swab and 12 tape sample	qPCR Bacterial Culture S. aureus CFU
Day 35	1 Swab from each treatment site	qPCR Bacterial Culture S. aureus CFU
Day 42	1 Swab from each treatment site	qPCR Bacterial Culture S. aureus CFU

If the atopic dermatitis has cleared completely in a treatment site, the investigator is to use clinical judgment, anatomical landmarks and previously captured digital images to identify the specific location to be sampled.

Test Article Administration

All subjects will have approximately 27 applications of the assigned test articles applied to each treatment site by unblinded study personnel at the Day 1/Baseline, Day 7, Day 14 and Day 21 visits. Doses between visits will be applied by the subjects, or LAR, under the supervision of an unblinded treating investigator, or designee, during telemed visits on weekdays and unsupervised on weekends. Details of test article preparation are in the Pharmacy Instruction Manual, provided

separately. Approximately 0.1 ml of assigned test article will be applied to each treatment site (each site is approximately 100 cm^2). The product is to be air dried.

If technical or other logistical issues prevent a telemed connection (i.e., a weekday telemed is missed for any reason) the subject is to apply test articles unsupervised.

Concomitant medication and Excluded Therapy

Usage of prescription or over the counter topical or systemic medications will be reported during the subject's participation in the study. Subjects will be supplied with 1% Hydrocortisone Ointment to treat areas of A remote from the designated treatment sites.

Randomization

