8.5 Relationship of Adverse Events to Investigational Product

The following classifications should be used when evaluating the relationship of AEs and SAEs to the investigational product.

- 1. Unrelated: No relationship between the experience and the administration of investigational product; related to other etiologies such as concomitant medications or subject's clinical state.
- 2. Probably not related: The current state of knowledge indicates that a relationship is unlikely.
- 3. **Possibly related**: A reaction that follows a plausible temporal sequence from administration of the investigational product and follows a known response pattern to the suspected investigational product. The reaction might have been produced by the subject's clinical state or other modes of therapy administered to the subject.
- 4. **Probably related**: A reaction that follows a plausible temporal sequence from administration of the investigational product and follows a known response pattern to the suspected

investigational product. The reaction cannot be reasonably explained by the known characteristics of the subject's clinical state or other modes of therapy administered to the subject.

5. **Definitely related**: A reaction that follows a plausible temporal sequence from administration of the investigational product and follows a known response pattern to the suspected investigational product and can be confirmed with a positive re-challenge test or supporting laboratory data.

8.6. Intensity: Classification of Intensity of Adverse Event.

The following classifications should be used when evaluating the intensity of AE's and SAE's:

- 1. Mild: Awareness of sign or symptom, but easily tolerated
- 2. Moderate: Discomfort enough to cause interference with normal daily activities
- 3. Severe: Inability to perform normal daily activities
- 4. Life-threatening: Immediate risk of death from the reaction as it occurred
- 5. Death

PROCEDURES FOR ADVERSE EVENT RECORDING AND REPORTING

Emergency Sponsor Contact

In the event of a medical emergency (i.e., an event that requires immediate attention regarding the treatment of a subject, operation of the clinical study, and/or the use of investigational drug), investigational site personnel must immediately contact the Medical Monitor.

Medical Monitor Contact		
Name:	MD, MS, MPH (primary)	
Telephone:		
\times		
Name:	(secondary)	
Telephone:		

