Study subjects can withdraw their consent to have their clinical samples stored even after the sample has been shipped to the sponsor laboratory. A study subject should contact the Investigator or the Investigator's designee and ask for his/her sample to be withdrawn from the storage and destroyed. For samples that have been partially analyzed the remaining sample will be destroyed but the clinical site and DermBiont shall be entitled to retain and use any research results obtained prior to the withdrawal of consent.

Protocol Amendments

Protocol amendments that impact subject safety, change the scope of the investigation, or affect the scientific quality of the study must be approved by the IRB/IEC and submitted to the appropriate regulatory authorities before implementation of such modifications to the study.

In the event that the protocol needs to be modified immediately to eliminate an apparent hazard to a subject, DermBiont will amend and implement the protocol change and subsequently notify the regulatory authorities and/or the IRB/IEC, as appropriate.

The Investigator should not modify the protocol without agreement from DermBiont and prior review or approval by the IRB/IEC. Any deviations from the protocol should be documented by the Investigator or designee.

Obligations of the Clinical Investigator

The Investigator will agree to be responsible for the overall conduct of the study; for completing regulatory documents and documentation of training; for ensuring that the study is conducted according to the study protocol; for protecting the rights, safety and welfare of study subjects under their care; and for insuring data quality and integrity.

If any study responsibilities are delegated, the Investigator will be responsible for maintaining written documentation of who is designate to perform the specific responsibilities.

The study will be conducted by qualified study Investigators.

The Investigator or designees are responsible for qualified subjects and collecting samples. The Investigator or designees will be responsible for maintaining records of all samples collected and investigational product administrations; recording the subject's data on the source documents and CRFs; documenting the presence or absence of AEs following sample collection and investigational product applications and following the reporting requirements of any SAEs to the Sponsor and IRB/IEC.

Institutional Review Board/Independent Ethics Committee

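### The only compulsory study halt (6.4.3) is ambiguously joined and counted, and neither reading of the join gives a pre-specified trigger for a single related life-threatening or fatal event

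*Combined protocol and SAP*

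**What the plan says.** Section 6.4.3 (Stopping Rules) is the one place where the protocol makes a study-level halt compulsory. The sponsor, through its Medical Director or Chief Medical Officer, is to halt for a review of safety data on the following condition: "safety concerns noted for any reason and if one or more subjects experience two AE's assessed as a Grade 3 (severe) or higher". The sentence goes on to require that the two events be of the same type and considered at least possibly related to the investigational product.

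The intensity scale in 8.6 has five classes. Class 3 is severe, class 4 is "Life-threatening: Immediate risk of death from the reaction as it occurred", and class 5 is death. Section 6.4.3 speaks of grades and 8.6 of numbered intensity classes; the match is implied, not stated.

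Other provisions bear on the same situation:

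- Section 6.4.2: "Study discontinuation is at the discretion of the Sponsor or the Investigator". The listed grounds include "Occurrence of unusual AEs in terms of their nature, severity, causality, duration, or unexpected incidence".
- Section 6.4.1: "The Investigator has the right to terminate participation of a subject at any time", with perceived safety risk among the grounds.
- Emergency Sponsor Contact: in a medical emergency, "investigational site personnel must immediately contact the Medical Monitor".
- Obligations of the Clinical Investigator: the duties include "following the reporting requirements of any SAEs to the Sponsor and IRB/IEC".
- Protocol Amendments: the sponsor may change the protocol at once to remove an apparent hazard and notify afterwards.

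On exposure, Test Article Administration states: "All subjects will have approximately 27 applications of the assigned test articles applied to each treatment site". One of each subject's two sites receives DBI-001, so every subject is exposed to the live bacterium.

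**The concern.** A compulsory stopping rule should give the same answer whoever applies it. Here two officers could read the sentence differently and reach opposite decisions on the same event.

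The rule also asks for the same count of two whether the event is severe, life-threatening or fatal. The events that most need a prompt pause therefore have no trigger of their own. After a first related event of intensity 4 or 5, whether dosing must pause depends on how *and if* is read and on whether a concern is formally noted.

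The product is a live organism applied daily, without supervision at weekends, in subjects from 12 years of age. The Rationale cites a single-application pilot in atopic dermatitis and 28 daily applications in tinea pedis. Of the experience cited there, none is repeated daily dosing on atopic dermatitis lesions.

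**Working it through.** The plan states no operating characteristics for the stopping rule, so there is no figure to reproduce. The check is a reading of the text.

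**Step 1: how the two conditions join.** If *and if* joins two requirements, a noted concern and the count must both be present. If it introduces a second trigger, either is enough. The phrase *for any reason* and the repeated *if* favour the second. So does redundancy: two related severe events of one type would already be a safety concern, which would leave the first condition little to do if both were required.

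**Step 2: how the two events are counted.** One or more subjects having two events can mean two in the same subject, or two in total across subjects. The text does not settle this.

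**Step 3: apply each combination to three cases.** All events are taken as related to the product; in the second and third cases they are also of the same type.

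| Case | Both required, count within subject | Both required, count across subjects | Separate triggers, count within subject | Separate triggers, count across subjects |
|---|---|---|---|---|
| One event of intensity 4 or 5 | No halt, even if a concern is noted | No halt, even if a concern is noted | Halt only if a concern is noted | Halt only if a concern is noted |
| Grade 3 once in each of two subjects | No halt, even if a concern is noted | Halt only if a concern is noted | Halt only if a concern is noted | Halt on the count |
| Grade 3 twice in one subject | Halt only if a concern is noted | Halt only if a concern is noted | Halt on the count | Halt on the count |

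The columns are not equally plausible, and nothing here rests on how many of them give a particular answer. The first row is what matters: the count is 1, the threshold is 2, and no combination produces a halt from the count. On the within-subject count, deaths alone could never reach the threshold, because a death cannot recur in the same person.

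**Step 4: look for a compulsory halt elsewhere.** Section 6.4.2 permits stopping the study. Section 6.4.1 permits ending one subject's participation. The emergency and SAE provisions require contact and reporting. The amendment provision allows rapid change. None of them obliges anyone to halt the study. General Statistical Considerations states that no interim analyses are planned.

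**The case against.** The strongest reply is that the better reading already works. If the triggers are separate, a related death noted as a safety concern compels a halt, and it is hard to imagine a sponsor not noting it. That is fair as a prediction of conduct. It does not remove the ambiguity, because on the literal reading even a noted concern compels nothing, and it leaves the gravest case resting on an undefined term.

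A second reply is that grade and causality are themselves judgements, so no trigger is fully objective. This stands. Section 8.5 defines even a possible relationship partly by a known response pattern, so a first, novel reaction could fail the definition. A single-event trigger that requires relatedness has that limit.

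A third is that the trial has other protection: immune-suppressed subjects are excluded, the strain is described as susceptible to common antibiotics, and earlier use was well tolerated. This also stands, and it limits the weight of the point.

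A reader might infer that subjects are unprotected, or that dosing would carry on after a related death. The documents do not support that: the sponsor or investigator may stop the study under 6.4.2 on grounds that name severity and causality, and emergencies and SAEs must be escalated. A reader might also infer that all the remaining subjects (20 − 1 = 19) would still be dosing. That is only an upper bound, which needs full enrolment and everyone within the dosing period at once; the documents do not say so.

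**Conclusion.** The point holds as a defect in the wording and coverage of a safety rule, and it should be corrected. Section 6.4.3 is open on the join and on the count. One related event of intensity 4 or 5 compels no halt on the literal reading; on the reading the wording favours, it does so only through the undefined concern condition.

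The conclusion assumes that the grades in 6.4.3 are the intensity classes in 8.6, and that no document outside the protocol text contains a further compulsory halt. It does not depend on any event rate. The documents give none, so the frequency of the situation cannot be stated.

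**What to change.** Keep the opening of the 6.4.3 sentence, including the named officers and the compulsory verb, and replace its conditions with three limbs joined by *or*:

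- (a) a safety concern is noted, whatever its cause;
- (b) any single AE of intensity 4 (life-threatening) or 5 (death) under 8.6 occurs and is judged at least possibly related to the IP;
- (c) two or more AEs of Grade 3 or above, of one type and judged at least possibly related, occur in the same subject or in different subjects.

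Limb (a) should stay compulsory. Making it a matter of whether an officer thinks a halt is warranted would weaken the rule on the reading the present wording favours. Limb (b) still depends on the investigator's causality call under 8.5; a novel event that fails that definition would fall to limb (a).

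The cost is modest but real. The change affects subject safety, so Protocol Amendments requires IRB/IEC approval and regulatory submission before it takes effect. A temporary halt becomes somewhat more likely: through (b) on any reading, through (c) if events are now counted within subjects or both conditions are now required, and through (a) if both are now required. A halt would interrupt daily dosing and the scheduled assessments from Day 7 to Day 42 for subjects on treatment, so there is some cost in data. The documents give no rates from which to quantify it. The sample size is unaffected.

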dose and mode	investigator(s) at respective the investigational site(s) on Baseline/Day 1 followed by weakly applications on Days $7(\pm/2)$, $14(\pm/2)$, and $21(\pm/2)$)
01 administration	The daily applications between visits will be applied by the subjects or
aummistr ation	LAR under the supervision of a designated treating investigator(s) or
	delegate(s), during a telemed visit on weekdays and unsupervised on
	weekends.
	Approximately 0.1ml of the assigned test articles will be applied to
	designated treatment sites.
	1mL vial of DBI-001 gel contains 10 ⁷ -10 ⁹ CFU/mL of
	Approximately 0.1mL applied to a treatment area that is approximately 100
	cm^2 will contain approximately 10^{4-6} CFU per cm^2 of
	Approximately 56 days (+/-4) including up to 14 days from Screening
Duration of	Visit to Baseline Visit, a 28 $(+/-2)$ day treatment period followed by a 14
Trial	(+/-4) day post treatment follow up.
Statistical	All subjects who are randomized and treated with test article will be
methods	included in the Intent-to-Treat analysis set.
	All subjects who are randomized, receive at least one (1) confirmed dose
	of test article, and have at least one (1) post-baseline safety assessment
	will be included in the Safety analysis set.

	The evaluation of S. aureus qPCR and CFU abundance will be performed on all subjects and separately in a modified intent to treat (MITT) population defined as subjects with bilateral abundant S. aureus at baseline as detected by qPCR. A MITT population defined as all subjects with detected by qPCR at one or more time points in samples obtained from one treatment targeted site but no detected in any sample from the contralateral treatment targeted site at any time point during the trial will also be evaluated.
	Linear interpolation of efficacy variables will be performed using observed data that precedes and follows the off-schedule visit, if present. The last observation will be carried forward if all the data subsequent to the off- schedule value is missing.
	No adjustments for multiplicity will be made; p-values are primarily presented for descriptive purposes.

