Study Design/Type	This is a randomized, observer blinded, Aqueous Gel-controlled, daily application for 4 weeks, within-subject, bilateral comparison trial examining the effect of DBI-001 Gel vs. Aqueous Gel on the clinical ADSI scores and the abundance of S. aureus of comparable bilateral target sites of AD as well as signs and symptoms of local tolerability on treated sites in subjects.
	Subjects meeting the inclusion/exclusion criteria and having moderate to severe AD lesions at screening and baseline/Day 1 will be enrolled into the study.
	In an observer-blinded fashion, each subject will have two sites randomly assigned to have either DBI-001Gel or Aqueous Gel applied to the designated treatment targeted sites.
	After Screening, Study visits will occur at Day 1 Baseline then Days 7 (± 2), 14 (± 2), 21 (± 2), 28 (± 2), 35 (± 4), and 42 (± 4).
	At each study visit, the following procedures will be conducted: clinical assessment of signs and symptoms of AD, ADSI clinical scoring, clinical signs and symptoms of erythema, pruritus, exudation, excoriation, lichenification. pain, burning, or stinging, and collection of microbiologic samples. Photos of both treatment sites will be taken on all visits except the Screening Visit.

Table 1.Schedule of Events.

Evaluation	^a Screen (- 14 Day to day 0)	Day 1 Baseline	Day 7 (±2)	Day 14 (±2)	Day 21 (±2)	Day 28 (±2)	Day 35 (±2)	Day 42 (±4)
		•	Trea	tment	•	•	Fol	low-up
Demographics	X							
Inclusion/Exclusion	X							
Urine Pregnancy test (For Women of childbearing potential)	X			X				Х
Confirm Compliance with Treatment Site Restrictions ^b		Х	Х	Х	Х	Х	Х	Х
Medical History	X							
Concomitant Medication Query	Х	Х	Х	Х	х	Х	Х	Х
Adverse Events	X	X	Х	Х	Х	Х	Х	Х
Clinical Assessment of Local Tolerability		Xc	Х	X	X	X	X	X
Calculate ADSI Scores based on Signs and Symptoms of AD	x	x	X	Х	X	X	X	X
Digital Images of Both Treatment Sites		X	X	Х	X	X	X	X
PBS Swabs from both Sites		Х	Х	Х	Х	Х	Х	Х
Sample both Sites		X				X		
Apply Test Articles After all Evaluations and Sampling		X	X	Х	X			
Collect Returned Used and Unused Test Articles			Х	Х	Х	Х		
Dispense Test Articles for Home Application		Х	х	Х	х			
Review Treatment Site Restrictions		X	X	Х	X			
Review Procedures for Telemed Visits		X						
Dispense 1% Hydrocortisone Ointment as Needed		Х	x	Х	x	X	X	X
Appointment for Next Clinic Visit and Telemed ^a Visits	X ^a	X	Х	X	X	Х	X	

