^a Screening and Baseline visits can be on the same day only if *all* eligibility criteria are met and *all* required Screening and Day 1/Baseline tests and tasks are completed on the same day.

^b Except for the Day 28, 35, or 42 visits, if violations of treatment site restrictions prior to the visit are reported, details of the violation should be recorded in the CRF and the visit should be completed including evaluations and sampling.

^c On Baseline/Day 1, local tolerability is to be assessed 30-minutes after application of test articles.

For the Day 28, 35, and 42 Visits:

If violations of treatment site restrictions reported occurred more than 24 hours prior to the visit at the Day 28, 35, or 42 visits, details of the violation should be recorded in the CRF and the evaluations and sampling completed as scheduled.

If violations of treatment site restrictions less than 24 hours prior to the visit is reported at the Day 28, 35, or 42 visits, details of the violation should be recorded in the CRF. Evaluations can be completed but an additional visit 24-48 hours after the violation should be scheduled for sample collections.

Details on sampling sites are in Table 2 and the Collection Sampling, Storage, Shipping Procedure, provided separately.

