6. Technical ability and willingness to self-apply, or LAR to apply, test articles during telemed visits with the study staff.

7. Willingness to discontinue use of systemic AD treatments and topical treatments to the target areas for the duration of the study unless specifically permitted by the Investigator.

8. Willingness to comply with test site restriction for 12 hours prior to all office visits including the Baseline visit and for 12 hours after each treatment application. These treatment site restrictions include:

a. No washing of test sites with any cleansers or soaps. Water passing over the areas during showering is acceptable.

b. No rubbing the test sites with a washcloth, towel, luffas. Pat dry after showering is acceptable.

c. No recreational activities in chlorinated or chemically treated water such as swimming pools, hot tubs, and spas.

d. No tight or form fitting clothing covering the treatment areas.

e. No sunbathing or use of suntan parlors or tanning beds.

f. If participating in physical activities resulting in heavy perspiration only pat dry test site areas with towel if needed.

g. Any activity that in the opinion of the investigator might alter the quality of the samples collected or risk removal of the test article.

9. Willingness to undergo the following washout periods:

a. Washout of 2 weeks prior to the Baseline visit for topical treatments used on the two treatment target sites, including but not limited to: antibacterial products, anti-inflammatories (e.g., corticosteroids, tacrolimus, Pimecrolimus). Other than the two treatment sites, topical medications may be used before/during the duration of the study. Subjects will be provided 1% hydrocortisone for treating non-target areas during the trial.

b. Washout of 4 weeks prior to the Baseline visit for systemic treatments for AD, including but not limited to corticosteroids (oral or intramuscular injections), systemic immunomodulators or immunosuppressors (e.g., methotrexate, cyclosporine, hydroxychloroquine), antibiotics (oral or injected, if required to treat a medical condition short duration of oral antibiotics (≤ 10 days) are permitted after randomization) c. Washout of 2 weeks prior to the Baseline visit for bleach baths.

d. Washout of 2 weeks prior to the Baseline visit for phototherapy.

10. No history of allergy to at least two of the following classes of antibiotics:

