6.5.2 All Other Visits

Study visit assessments and sample collections will be conducted as presented in Tables 2 and 3.

The Screening and Day 1/Baseline visit can be combined for subjects meeting *all* eligibility requirements and only if *all* Screening and Day 1/Baseline tests and tasks can be completed on the same day.

Day 1/Baseline visit:

- 1. Confirm compliance with treatment site restrictions.
- 2. Record any changes in concomitant medications.
- 3. Record adverse event, if any.
- 4. Blinded evaluating investigator complete clinical assessment of severity of signs and symptoms of AD prior to application of test article.
- 5. Calculate ADSI score of both potential treatment sites if the Screening visit was on an earlier date. At Baseline, if ADSI eligibility criterion is no longer met, the subject is to be withdrawn from the study prior to sample collection and test article application.
- 6. Digital images of both treatment sites.
- 7. Collect PBS swabs from both treatment sites.
- 8. Collect samples from both treatment sites.
- 9. Unblinded treating investigator, or designee, to train subjects and/or LAR on method for selfor LAR to apply with a training vial.
- 10. Unblinded treating investigator, or designee, apply test articles after all evaluations and sampling have been completed.
- 11. Blinded evaluating investigator complete clinical assessment of local tolerability (severity pain, burning, or stinging in addition to pruritus, erythema, exudation, excoriation, and lichenification) 30-minutes after application of test articles to both treatment sites.
- 12. Review treatment site restrictions.
- 13. Review procedures for telemed visits.
- 14. Dispense 1% hydrocortisone ointment as needed.
- 15. Schedule appointment for Day 7 clinic visit and telemed visits.

Detailed instructions for sample collection, storage, and shipping are in the Collection Sampling, Storage, Shipping Procedure (CSSSP) provided separately. If violations of treatment site restrictions prior to the visit are reported details of the violation should be recorded in the CRF and the visit should be completed including evaluations and sampling.

DermBiont

Day 7 (±2)

- 1. Confirm compliance with treatment site restrictions.
- 2. Record any changes in concomitant medications.
- 3. Record adverse event, if any.
- 4. Blinded evaluating investigator complete clinical assessment of severity of signs and symptoms of AD.

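### A recent treatment-site violation defers sampling at Days 28, 35 and 42 but not at Baseline, the only pre-treatment sample and the sole basis for S. aureus MITT membership

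*Combined protocol and SAP*

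**What the plan says.** Inclusion criterion 8 asks for "Willingness to comply with test site restriction for 12 hours prior to all office visits including the Baseline visit". The synopsis gives sample quality as one reason for the restrictions.

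Three places set the rule for a violation before Baseline, and they agree:
- Study Visits (after section 6.4.3) treats reported "violations of treatment site restrictions occurred prior to the visit at Screening, Day 1 / Baseline, Day 7, 14 or 21" alike: record the violation, then evaluate and sample as scheduled.
- Table 1, footnote b, begins "Except for the Day 28, 35, or 42 visits, if violations of treatment site restrictions prior to the visit are reported" and gives the same instruction.
- Section 6.5.2, Day 1/Baseline, repeats it: "details of the violation should be recorded in the CRF and the visit should be completed including evaluations and sampling".

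For a violation less than 24 hours before Day 28, 35 or 42, evaluations may be completed, but "an additional visit 24-48 hours after the violation should be scheduled for sample collections".

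Table 2 (section 6.6.3) lists no Screening sample. Day 1, with a swab and tape samples, is therefore the only pre-treatment measurement. The synopsis (Statistical methods) defines the S. aureus MITT as "subjects with bilateral abundant S. aureus at baseline as detected by qPCR". It also says that S. aureus abundance is evaluated in all subjects.

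**The concern.** The protocol judges a recent violation serious enough to hold back a follow-up sample, yet it accepts the same flaw in the sample to which later ones are compared. A flawed Day 7 swab damages one time point. A flawed Day 1 swab enters every comparison that subtracts baseline, and can also change who is in the MITT. No reason is given for the difference. The only consequence described for a failed compliance check at Day 1 is a CRF entry.

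The visit order gives limited support to the 12-hour restriction. In Table 1 the row "Review Treatment Site Restrictions" is first marked at Day 1. In the Day 1 list, compliance is confirmed at item 1, samples are taken at items 7 and 8, the test articles are applied at item 10, and the restrictions are reviewed at item 12. If Screening and Baseline share a day, the 12 hours have already passed when the subject arrives.

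At stake are the secondary S. aureus results, in a trial of about 20 subjects with fewer in the MITT.

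**Working it through.** **1. The rules side by side**

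| Visit | Recent violation reported | Role of the sample |
|---|---|---|
| Day 1 | Record, sample as scheduled | Reference for change; decides MITT |
| Days 7, 14, 21 | Record, sample as scheduled | Own time point only |
| Days 28, 35, 42 | Under 24 h: sampling deferred to 24-48 h after the violation | Own time point only |

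The plan states no figure to reproduce here: the sample size of about 20 rests on clinical judgement, with no effect size or SD.

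**2. Effect on the endpoint.** On the log10 scale, let D be the change at the DBI-001 site minus the change at the gel site. Suppose a violation lowers the Day 1 values by a (DBI-001 site) and g (gel site). Then:
- within-site change rises by a or g, which hides a reduction;
- the paired difference becomes D + (a − g);
- if a = g, D is unchanged;
- if a ≠ g, the error is the same at every visit where baseline is subtracted. Because side is randomised and the violation precedes treatment, the mean of (a − g) is zero. The result is noise, not bias.

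One subject in 20 is 1/20 = 5% of pairs, and more in a smaller MITT.

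**3. Within-site change, illustrated.** The mean shift is (share of subjects affected) × (log10 loss) when both sites are affected: 0.10 × 1 = 0.10 up to 0.30 × 2 = 0.60 log10. It is half that when one site, chosen at random, is affected.

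**4. MITT membership, illustrated.** The documents give no cutoff for abundant, no violation rate and no effect of a violation. Assumed: log10 abundance with mean 4.5, between-subject SD 1, site SD 0.5; cutoff 3 or 4. Share of affected, truly bilateral subjects wrongly excluded (400,000 simulated subjects per row):

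| Cutoff | Log10 loss | One site affected | Both sites affected |
|---|---|---|---|
| 3 | 0.5 | 9% | 14% |
| 3 | 1 | 23% | 33% |
| 3 | 2 | 62% | 73% |
| 4 | 0.5 | 20% | 31% |
| 4 | 1 | 45% | 59% |
| 4 | 2 | 85% | 92% |

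**5. Precision, illustrated.** Assumed: true paired difference of 1 log10, SD 1.2, two-sided signed-rank test at 0.05, 2,000 simulated trials per setting (Monte Carlo error about 0.01).

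| Setting | Power, n = 12 | Power, n = 20 |
|---|---|---|
| No Baseline affected | about 0.70 | about 0.93 |
| One site lowered by 1 log10 in 10% to 30% of subjects | 0.68 to 0.63 | 0.91 to 0.88 |
| One site lowered by 2 log10 in 10% to 30% of subjects | 0.61 to 0.46 | 0.87 to 0.71 |
| Both sites lowered equally | unchanged | unchanged |

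The mean paired difference stayed at about 1.0 log10 in favour of DBI-001 in every setting, as step 2 predicts.

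**6. Why MITT losses matter.** The smallest two-sided signed-rank p-value with n non-zero pairs is 2/2^n: 2/32 = 0.0625 at n = 5 and 2/64 = 0.031 at n = 6. The MITT test cannot reach 0.05 with fewer than six such pairs.

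**The case against.** Much of the case on the other side stands.

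- **Direction.** A reader might infer that a flawed baseline tilts the comparison between products. It does not, by step 2. The sites are symmetrical, so soap or a pool would often affect both, and equal effects cancel. The signed-rank test also limits the influence of one aberrant pair.
- **Loss from analysis.** A subject who misses the MITT is not lost to the S. aureus results, because all subjects are evaluated as well.
- **All six visits.** The synopsis and section 4.2.2 specify change from baseline at six visits. Section 7.2.2 speaks only of differences at Day 28, and its other days omit Day 42. On that wording baseline may not be subtracted. The passages need reconciling; MITT membership depends on Baseline either way.
- **Prior notice.** It would be too strong to say that subjects hear nothing of the restrictions before Day 1. Criterion 8 lists them, and eligibility is reviewed at Screening. But the criterion asks for willingness, not compliance, and a same-day visit leaves no time to act on the notice.
- **What counts as a violation.** Before Day 1 nothing has been applied, so only the 12-hour pre-visit window applies; an activity 12-24 hours earlier breaks no rule. Item 8a in the synopsis starts the soap ban at the Baseline visit, so soap used just before it is ambiguous there.
- **Importance.** The endpoints are secondary, p-values are mainly exploratory, and a separate SAP is promised that might flag affected baselines. The text supplied describes no such flag.

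None of this explains why Baseline is treated less strictly than Day 42.

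**Conclusion.** The inconsistency is certain: three places in the protocol agree on it, and none gives a reason. Followed exactly, the plan can keep a distorted Day 1 sample that its own follow-up rule would have deferred. The possible effects are a shift in within-site S. aureus change, added noise when sites are affected unequally, and wrongful exclusion from the MITT.

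The size is unknown, because the violation rate and its effect on abundance are not in the documents; the figures above are illustrations on assumed values. The primary ADSI endpoint is untouched: it does not use these samples, and ADSI evaluations may go ahead at Days 28, 35 and 42 after a violation too. This is a worthwhile, inexpensive correction to secondary endpoints, not a threat to the main result.

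**What to change.** 1. Take Day 1/Baseline out of the record-and-proceed group in Study Visits, Table 1 footnote b and the Day 1 text of section 6.5.2. If item 1 of the Day 1 list shows a violation of the 12-hour pre-Baseline restriction, defer Baseline sampling to 24-48 hours after the violation, as the existing rule does for later visits. The rest of Day 1 moves with it, because section 6.5.2 already requires the first application to follow all sampling.
2. Add "Review Treatment Site Restrictions" to the Screening list in section 6.5.1 and to the Screening column of Table 1.
3. Apply the same compliance check to combined Screening/Baseline visits.
4. Reconcile section 7.2.2 with the synopsis and section 4.2.2 on whether the S. aureus comparison uses change from baseline and includes Day 42.

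The cost is amendment wording, an occasional delay of one or two days to Day 1 before any test article is applied, and fewer same-day combined visits.
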